3 ANALYSIS SETS

3.1 Enrolled Analysis Set

The enrolled analysis set includes all patients who provided informed consent and met all study eligibility criteria as recorded in the eCRF. Patients who are later found to be incorrectly enrolled are also included this analysis set, but they may be excluded from some or all other analysis sets according to an agreement to be reached and documented in the Final Data Review Decisions document before database lock.

3.2 Safety Lead-in Evaluable Analysis Set

The Safety Lead-in Evaluable Analysis Set is defined as the first 6 patients enrolled in Stage 1 who completed at least 50% of the prescribed combination therapy doses during the first cycle of therapy (D1–28) or who received less than 50% of the prescribed combination therapy doses due to any Grade ≥ 3 related AE (including relationship to SRF617, Etrumadenant and/or Zimberelimab as Definite, Probable, and/or Possible) during the first cycle of therapy (D1–28).

This analysis set will be used to assess the preliminary safety of the combination therapy in the Safety Lead-in Period.

3.3 Safety Analysis Set

The Safety Analysis Set is defined as all patients who received any amount of SRF617. This analysis set will be the primary analysis set for all safety endpoints, excluding safety lead-in evaluation.

3.4 Response-Evaluable Analysis Set

The Response-Evaluable Analysis Set is defined as all enrolled patients who received SRF617 and had at least 1 post-Baseline response assessment (including PSA assessment and/or tumor assessment) or who discontinued the treatment phase because of radiographic or symptomatic disease progression (including death caused by disease progression) within 6 weeks (+ 2-week window) of the first dose of SRF617. This analysis set will be the primary analysis set for the primary efficacy endpoint and other efficacy endpoints.

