#### **9.2.3. Response-Evaluable Analysis Set**

The Response-Evaluable Analysis Set is defined as all patients at Baseline who received study drug and had at least 1 post-Baseline response assessment or who discontinued the treatment

---

phase because of radiographic or symptomatic disease progression (including death caused by disease progression) within 6 weeks (+ 2 week window) of the first dose of study drug. This analysis set will be the primary analysis set for the primary efficacy endpoint and other efficacy endpoints.

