#### **9.2.4. Intent-to-Treat Analysis Set**

The Intent-to-Treat Analysis Set is defined as all enrolled patients who received any amount of study drug.

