1.1 Discrepancies Between the SAP and the Protocol

Surface (sponsor) terminated the study when 15 subjects received treatment. The abbreviated analysis will focus on safety assessments.

Pharmacokinetics Analysis Set, Blood Biomarker Analysis Set, Tumor Biopsy Analysis Set, and Immunogenicity Analysis Set, and corresponding analyses are removed from this SAP.

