10 EFFICACY ANALYSIS

The assessment of tumor response is based on PCWG3 criteria as well as RECIST v1.1 being evaluated by Investigators. The summary will be presented using response-evaluable analysis set.

Assessment of response will be evaluated by computed tomography or magnetic resonance imaging of chest/abdomen/pelvis and bone scan every 12 weeks. PSA assessment will be performed every cycle. Patients should continue past PSA progression until clear radiologic progression or clinical progression (eg, symptomatic or physical deterioration in the absence of radiographic progression that meets PCWG3 criteria). The overall PCWG3 criteria and RECIST v1.1 Response visit responses include Complete Response (CR), Partial Response (PR), Stable Disease (SD), Progressive Disease (PD), Non-CR/Non-PD, Not Evaluable (NE), Not Assessed (NA),

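### The only response rate kept has no all-treated counterpart, and SAP 3.1 allows treated patients to be taken out of a Safety Set that SAP 3.3 defines without exception

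*SAP*

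**What the plan says.** **Response rate.** SAP version 2.0 keeps the Primary Composite Response Rate and drops the other efficacy summaries (Modification History; SAP 10.1.4). SAP 10 fixes the population: "The summary will be presented using response-evaluable analysis set". Under SAP 3.4 there are two ways into that set. The patient received SRF617 and "had at least 1 post-Baseline response assessment (including PSA assessment and/or tumor assessment"), or the patient stopped treatment for radiographic or symptomatic progression, including death from progression, within 6 weeks (plus a 2-week window) of the first dose. This follows Protocol 9.2.3, which says of the Response-Evaluable set: "This analysis set will be the primary analysis set for the primary efficacy endpoint and other efficacy endpoints".

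Protocol 9.2.4 also defines an all-treated set: "The Intent-to-Treat Analysis Set is defined as all enrolled patients who received any amount of study drug". The protocol assigns it no analysis, and SAP section 3 does not carry it over.

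**Safety Set.** SAP 3.3 reads: "The Safety Analysis Set is defined as all patients who received any amount of SRF617". SAP 3.1 says of the Enrolled set: "Patients who are later found to be incorrectly enrolled are also included this analysis set". It then adds that "they may be excluded from some or all other analysis sets according to an agreement to be reached and documented" before database lock. SAP 11 uses the Safety Set for every safety analysis except the lead-in, and SAP 1.1 says of the shortened report: "The abbreviated analysis will focus on safety assessments".

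**The concern.** The Response-Evaluable rule treats early failures unequally. A patient who progresses before any assessment stays in the denominator. One who leaves before any assessment because of toxicity, withdrawal, loss to follow-up or a death not due to progression does not. None of these patients can be a responder, so omitting the second kind can only raise the rate when there is at least one responder. With no responders it raises the upper confidence limit instead. No all-treated rate is planned beside the result to show whether this happened.

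The SAP 3.1 clause is a separate problem of internal consistency. For a treated patient later found ineligible, 3.3 requires inclusion in the Safety Set and 3.1 permits exclusion. The SAP gives no criterion for which enrollment error justifies exclusion from which set. SAP 6.3 lists enrollment of an ineligible subject as a possible major deviation but does not tie it to set membership. Using the clause would take that patient's adverse events out of the tables that are the focus of the report. The same clause also reaches the Response-Evaluable set. Because the trial is open-label with Investigator-assessed response, an exclusion agreed shortly before lock could be made with outcomes known.

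**Working it through.** **Design figures.** With 17 + 23 patients, success at 8 or more responses, and continuation at 2 or more responses in Stage 1, the probability of success is the sum over x ≥ 2 of P(X₁ = x; 17, p) × P(X₂ ≥ 8 − x; 23, p). This gives 0.0399 at p = 0.10 and 0.934 at p = 0.30, matching the stated 0.040 and 0.93. Those figures are not in dispute.

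**Who can fall out of the Response-Evaluable set.** PSA is scheduled on Day 1 of every cycle and at End of Treatment (Protocol Table 2), and one post-baseline value is enough. A patient is lost only by leaving before the first such value. The protocol allows two routes:
- consent withdrawal, after which no further evaluations are made (Protocol 4.8);
- an End of Treatment visit within 2 weeks of the baseline PSA, when the test need not be repeated (Table 2, note a).

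The gap is therefore narrow and may be empty.

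**Inputs for the size.** Treated: 15 (SAP 1.1 and 2), all assumed to have received SRF617. Null rate: 10% (SAP 2.3). Intervals: 80% and 95% Clopper-Pearson, with a one-sided exact test against 10% (SAP 10.2.1). Limits are rounded outward to one decimal (SAP 4.2). The responder count k is not in the documents, so k = 0 to 6 is an assumed range. One omitted patient is assumed, giving n = 14.

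**Rate and p-value.** Rate = k/n; p = P(X ≥ k) for X ~ Binomial(n, 0.10).

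| k | k/15 | k/14 | shift (points) | p, n = 15 | p, n = 14 |
|---|---|---|---|---|---|
| 1 | 6.7% | 7.1% | 0.48 | 0.7941 | 0.7712 |
| 2 | 13.3% | 14.3% | 0.95 | 0.4510 | 0.4154 |
| 3 | 20.0% | 21.4% | 1.43 | 0.1841 | 0.1584 |
| 4 | 26.7% | 28.6% | 1.90 | 0.0556 | 0.0441 |
| 5 | 33.3% | 35.7% | 2.38 | 0.0127 | 0.0092 |
| 6 | 40.0% | 42.9% | 2.86 | 0.0022 | 0.0015 |

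**Intervals, rounded outward.**
- 4/15: 80% CI 12.1 to 46.4, 95% CI 7.7 to 55.2.
- 4/14: 80% CI 13.0 to 49.2, 95% CI 8.3 to 58.2.
- With no responders, the upper 80% limit goes from 14.3% (n = 15) to 15.2% (n = 14), and the upper 95% limit from 21.9% to 23.2%.

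**Safety Set.** Suppose one treated patient is removed under SAP 3.1. An event seen only in that patient goes from 1/15 = 6.7% to 0/14. An event seen in that patient and one other goes from 2/15 = 13.3% to 1/14 = 7.1%.

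**The two SAP clauses together.** Section 3.3 has one condition, receipt of SRF617, and no exception. Section 3.1 reaches every set other than the Enrolled set. Nothing in the SAP says which prevails.

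**The case against.** Using the Response-Evaluable set is a choice made in the protocol, and the Stage 1 rule is itself written for evaluable patients. The set is close to all-treated, since a single PSA qualifies and early progressors are kept. The protocol gives the ITT set no analysis, so its absence from the SAP breaks no promise. The Safety Set size is tabulated (SAP 6.1), so a reader with the responder count could rebuild the all-treated rate and recompute the intervals and p-value. The example with 4 responders is the only count from 1 to 6 at which one omission takes p across 0.05. The SAP sets no significance level, and the trial ended for business reasons without Stage 2.

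On the Safety Set, SAP 3.1 is permissive and requires a documented agreement. Section 3.3 could be read as the specific rule that governs. The criteria may sit in the Final Data Review Decisions document or the deviation plan, which are not available here. Any exclusion would show in the set counts and in the deviation listing for all treated patients.

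Most of this stands as a limit on weight. The primary set should not change, and the 0.05 crossing deserves no emphasis. It does not remove either point. Rebuilding the rate works only if nobody was removed under 3.1, and the matching intervals and p-value would still not be reported. No text says that 3.3 overrides 3.1, and being able to see an exclusion does not settle which definition applies.

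**Conclusion.** Both parts hold. The only response result is planned on a set that can omit treated patients who cannot be responders, with no all-treated figure beside it. SAP 3.1 as worded permits an exclusion that SAP 3.3 does not.

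The importance is low to moderate. For one omitted patient, the rate rises by 0.5 points (1 responder) to 2.9 points (6 responders). At 4 responders the shift is 1.9 points against a 95% interval about 47 points wide. These sizes rest on an assumed responder count and an assumed single omission. The documents do not show that any of the 15 treated patients is unassessed, or that any exclusion under 3.1 is planned. The conflict between 3.1 and 3.3 rests on the wording alone and needs no assumption.

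**What to change.** Keep the Response-Evaluable set as primary and make two edits.

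1. In SAP 10.2.1, add the composite response rate with its 80% and 95% exact intervals and one-sided p-value for all treated patients (the Safety Set, 15 as of 19JUN2023), counting those without a post-baseline assessment as non-responders.
2. In SAP 3.1, add one sentence stating that no patient who received SRF617 is excluded from the Safety Set or from the all-treated efficacy result.

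The cost is one extra column in one table and one sentence. The all-treated rate may be slightly lower than the primary one, or identical if every treated patient is evaluable, in which case the column shows exactly that.

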4 GENERAL CONSIDERATIONS

4.1 Programming Environment

Unless otherwise specified, all analyses will be conducted using SAS® version 9.4 or later.

4.2 General Statistical Methods

The statistical analyses will be presented for the different analysis sets being defined in Section 3.

Descriptive Summaries:

In general, numerical variables will be summarized using descriptive statistics, displaying the number of patients in the analysis set, the number of patients with data, sample mean, sample standard deviation (calculated as the square root of an unbiased variance estimate), sample median, minimum (min) and maximum (max).

Categorical variables will be summarized by using frequency counts and percentages. In addition, the number of patients with missing values will be displayed. Unless otherwise specified, the denominators used for calculating sample proportions will be the number of patients in the specified statistical analysis set (or a subset of the statistical analysis set under use).

Presentation Conventions:

Means and medians will be presented by 1 additional decimal place and standard deviation will be presented by 2 additional decimal places than the original data. Minimum and maximum values will be presented using the same number of decimal places as the original data. If not otherwise stated, percentages will be presented to 1 decimal place. However, when the percentage (or estimated proportion) is 100% exactly, no decimal place will be shown, whereas a presented 100.0% implies that the percentage is in the half-open interval [99.95%, 100%). The number of decimal places may be adjusted, e.g., if the above default choices may lead to misinterpretation of the presented data.

In general, rounding will only occur when presenting data but not when analyzing data. By default, presented data will be rounded to the nearest required presentation precision, with a half-up tie-breaking rule. However, when presenting confidence intervals, the lower interval limit will always be rounded down and the upper interval limit will always be rounded up in order preserve the claimed (exact or asymptotic) confidence level. When either limit is outside of the parameter space (e.g., below 0 or above 1 for proportions), the interval will be truncated at the boundary of the parameter space.

If the number of patients in a category is 0, then percentage will not be displayed, and only a count of 0 will be shown. However, structural zeros (e.g., when the count is deemed to be 0 before obtaining actual data), missing data or inapplicable/unevaluable summaries will be presented as –, NA or NE.

In listings, data will be sorted by site and patient, and when appropriate by visit or other identifiers for sequence or type of observation.

4.3 Subgroups

Subgroup analyses will not be performed.

4.4 Multiple Comparison/Multiplicity

No multiplicity adjustment is planned.

5 DEFINITIONS & DATA HANDLING CONVENTIONS

5.1 Study Day, Duration, and Study Periods

Day 1 will be the date corresponding to the first administration of SRF617. Study Day will be computed as the given date minus the date of Day 1 +1 (i.e., Study Day = Date – Date of Day 1 + 1) for dates on or after date of Day 1. For study assessment or treatment prior to Day 1, Study Day = Assessment Date – Date of Day 1.

Unless otherwise specified, day is the primary time unit for derived time and durations. Derived time units include week=7 days, month=30.436875 days, and (Gregorian) year=365.2425 days=12 months. Thus, 1 month and 4 weeks are considered different.

Unless otherwise specified, duration of time is defined from the starting day through the ending day, inclusive of both boundary days.

Study periods are defined as follows:

- screening period: beginning on the day of informed consent, or Study Day -30, whichever is latest, and ending on Day -1.
- treatment period: beginning on Study Day 1 and ending on the date of EoT visit. In case that the EoT visit is missed for any reason, the treatment period will end on the 7th day since the last dose of any study drug.
- safety follow-up period: beginning on the first day after the treatment period and ending on the last day of the Safety Follow-up visit (or study discontinuation, whichever occurs first). Safety Follow-up visit is scheduled to be approximately 30 days after the last dose of SRF617, 30 days after the last dose of etrumadename, or 90 days (+ 7 days) after the last dose of zimberelimab (30 days after the last dose of zimberelimab if the patient initiates a new anticancer therapy), whichever is latest.

Unless otherwise specified, events in the screening period are considered as pre-treatment, and events in the treatment period or safety follow-up period are considered as on-treatment.

5.2 Analysis Visit Windows

Patient visits will be presented according to the nominal visit as obtained upon the eCRF. All values will be included in the patient data listings.

5.3 Data Derivation

Baseline and Change from Baseline

The baseline value is defined to be the last non-missing assessment prior to the first dose of SRF617. For assessments performed on Cycle 1 Day 1, if the time of the day is missing but scheduled time point is recorded as preinfusion or pre-dose, the assessment may be considered the baseline assessment for the respective study procedures. Unless otherwise specified, change from baseline (CFB) calculations for a treatment window assessment will be the applicable treatment window assessment minus the baseline assessment. If either the treatment window assessment value or the baseline value is/are missing, then CFB will be set to missing for descriptive analysis purposes, unless otherwise specified.

5.4 Missing Data

5.4.1 Partial or Missing Dates and Time

The missing component(s) of incomplete dates (e.g., start and/or stop dates of AE, concomitant medication) will be assumed as the most conservative value possible. In general, unless the available parts of the partial date preclude an AE to be treatment-emergent, the AE will be considered treatment-emergent; similarly, unless the available parts of the partial date preclude a medication to be concomitant, the medication will be considered as a concomitant medication.

For example, if the start date has a missing day value, the first day of the month will be imputed for study day computations, etc. If day is missing for an end date, the last day of the month will be imputed. If the start date has a missing month value, the first month of the year will be imputed for study day computations, etc. If month is missing for an end date, the last month of the year will be imputed. For determination of treatment-emergent status, the start date will be imputed as the date of the first dose of study drug, unless there is clear evidence (through comparison of partial dates/times) to suggest otherwise.

Date imputation will only be used for computational purposes such as treatment-emergent status, etc. Actual data values, as they appear in the original eCRFs, will be presented in the patient data listings. Non-monotone partial dates (e.g., day and month are non-missing but year is missing) need to be queried and resolved before DBL.

5.4.2 Other Missing Values

Every effort will be made to obtain required data at each scheduled evaluation from all patients who have been enrolled. In general, missing data will not be imputed and the data will be analyzed as they are recorded.

6 STUDY POPULATION, CONDUCT AND PATIENT DISPOSITION

6.1 Analysis Sets

The number and percentage of patients in each analysis set as defined in Section 3 will be descriptively summarized using the enrolled analysis set. Corresponding data listing will be provided using the enrolled analysis set.

6.2 Patient Disposition

The number and percentage of patients in the following categories will be descriptively summarized using the safety analysis set.

- SRF617 treatment ongoing
- SRF617 treatment discontinuation
- Reason for SRF617 treatment discontinuation
 - Death
 - Adverse Events
 - Progressive Disease
 - RECIST Progression, only
 - Clinical Progression, only
 - PSA Progression, only
 - Any combinations of the above
 - Other Progression
 - Non-compliance with study protocol
 - Physician Decision
 - Study terminated by sponsor
 - Withdrawal by subject
 - Lost to follow-up
 - Other
- Etrumadenant treatment ongoing
- Etrumadenant treatment discontinuation
- Reason for Etrumadenant treatment discontinuation
 - Death
 - Adverse Events
 - Progressive Disease
 - RECIST Progression, only
 - Clinical Progression, only
 - PSA Progression, only
 - Any combinations of the above
 - Other Progression
 - Non-compliance with study protocol
 - Physician Decision
 - Study terminated by sponsor
 - Withdrawal by subject
 - Lost to follow-up
 - Other
- Zimberelimab treatment ongoing
- Zimberelimab treatment discontinuation
- Reason for Zimberelimab treatment discontinuation
 - Death
 - Adverse Events
 - Progressive Disease
 - RECIST Progression, only
 - Clinical Progression, only

- PSA Progression, only
- Any combinations of the above
- Other Progression
- Non-compliance with study protocol
- Physician Decision
- Study terminated by sponsor
- Withdrawal by subject
- Lost to follow-up
- Other

- Study ongoing
- Study discontinuation
- Reason for study discontinuation
 - Death
 - Adverse Events
 - Progressive Disease
 - Non-compliance with study protocol
 - Physician Decision
 - Study terminated by sponsor
 - Withdrawal by subject
 - Lost to follow-up
 - Completed Safety Follow up visit
 - Other

Disposition of patients will be provided in a data listing using the safety analysis set.

6.3 Protocol Deviations

Protocol Deviation Management Plan (PDMP) version: 3.0 dated on 03Mar2023 defined the study specific procedures and responsibilities for managing Protocol Deviations (PDvs). The document listed the definition of Bioclinica Deviation Description and Deviation Area, as well the Deviation Category (major vs minor). Subject level protocol deviations will be documented in the Clinical Trial Management System (CTMS). Protocol Deviation Review meeting will review protocol listing for quality control.

Major deviations (Important Protocol Deviation, IPD) from the clinical protocol may include (if assessed as), but are not limited to:

- ICF/Subject Information
- Ineligible Subject Enrolled
- IMP Dose Error
- IMP Other Error
- Prohibited Medication
- SAE or AESI Reporting Failure

All protocol deviations (both major and minor) will be provided in a data listing for all treated patients.

7 DEMOGRAPHICS AND BASLEINE CHARACTERISTICS

7.1 Demographics

The following demographic characteristics will be descriptively summarized using the safety analysis set:

- Sex at birth
- Age (years, as reported in Demographics EDC)
- Age (\geq median vs. $<$ median; and \geq 70 years vs. $<$ 70 years)
- Race (American Indian or Alaska Native, Asian, Black or African American, Native Hawaiian or other Pacific Islander, White, Unknown, Other, Not Reported)
- Ethnicity (Hispanic or Latino, not Hispanic or Latino, not reported, unknown)
- ECOG performance status (0, 1)
- ALP at baseline (\geq median vs. $<$ median)
- LDH at baseline (\geq median vs. $<$ median)

Demographic characteristics will also be provided in a data listing using the safety analysis set.

7.2 Cancer History

The following primary and metastatic cancer history characteristics will be summarized using the safety analysis set:

- TNM stage at initial diagnosis
 - Pathological T category (T1, T2, T3a, T3b, T4, Unknown)
 - Regional lymph node N category (NX, N0, N1, Unknown)
 - Distant metastasis M category (cM0, cM1a, cM1b, cM1c, pM1a, pM1b, pM1c, Unknown)
- Castrate-Resistant Status (Chemical, Surgical)
- Gleason score at Diagnosis (6, 7, \geq 8)
- Type of Progression at Trial Entry
 - PSA only
 - Nadir PSA on last therapy (ng/ml)
 - Radiographic progression
 - Bone only
 - Bone with Nodal Disease
 - Nodal disease only
 - Visceral
- Distribution of metastatic disease
 - Metastatic Site Type
 - Pelvic nodal
 - Extra-pelvic nodal
 - Bone
 - Visceral
 - Volume
 - High (number of lesions \geq 4)
 - Low ($0 \leq$ number of lesions \leq 3)
- PSA at baseline (\geq median vs. $<$ median)
- Time since prostate cancer diagnosis (months), defined as time from the date of prostate cancer diagnosis to the date of first SRF617 dose

- Time since metastatic disease diagnosis (weeks), defined as time from the date of metastatic disease diagnosis to the date of first SRF617 dose
- Time since castrate resistance (weeks), defined as time from the date the disease became castrate resistant to the date of first SRF617 dose
- Mutation/genetic alteration analysis
 - Yes
 - No
- MSI status and MMR status
 - MSI-H (microsatellite instability-high)
 - MSI-L (microsatellite instability-low)
 - MSS (microsatellite stable)
 - dMMR (mismatch repair deficient)
 - Due to MLH1
 - Due to MSH2
 - Due to MSH6
 - Due to PMS2
 - pMMR (mismatch repair proficient)
- DNA Damage Repair (DDR) Alterations
 - ARD1A
 - ATM
 - BARD1
 - BRCA1
 - BRCA2
 - BRIP1
 - CDK12
 - CHEK2
 - FANCA
 - <insert all of Genes in the eCRF>
 - Other
- TMB
 - ≤10
 - >10
 - Unknown
- PD-L1 expression
 - Negative
 - Positive
 - n, mean, standard deviation, median, min, max
 - <1%, ≥1%
 - Unknown

Primary cancer history characteristics and tumor genomic alterations/protein expression will also be provided in a data listing using the safety analysis set.

